
Test Product, Dose, and Mode of Administration:
 
CUTAQUIG, human normal immunoglobulin for subcutaneous (SC) administration.
 
CUTAQUIG will be administered by SC infusion every week (± 2 days, Cohort 1 and Cohort 2), every other week (± 2 days, Cohort 3) at the doubled weekly dose. The dosing frequency will be determined by cohort assignment.
 
Patients will receive the same mg/kg body weight dose as their previous SCIG product prior to study entry.
 
If, during the study, a patient's body weight changes by $>5\%$ from the first infusion of IMP, the dose will be adjusted to keep a constant mg/kg body weight basis. Additional adjustments will be made by the Investigator at study visits if the patient's body weight changes $>5\%$ from the previous adjusted weight.
 
Each patient's CUTAQUIG dose may be individualized, if considered necessary by the Investigator, by titrating upward or downward.
 
Batch (lot) numbers will be reported in the final report of the study.

Duration of Treatment:
 
Individual patient participation will be approximately 30 to 32 weeks:
 
• Screening Period: 1 to 2 weeks*• Stabilization Period: 4 weeks**• CUTAQUIG Treatment Period: 24 weeks (6 months)• Termination Visit: 1 week after last CUTAQUIG infusion for Cohort 1 and Cohort 2; 2-weeks after last CUTAQUIG infusion for Cohort 3

Name of Sponsor/Company: Octapharma USA, [name]	
Name of Investigational Product: CUTAQUIG	Protocol Identification Code: SCGAM-06
Name of Active Ingredient: Human Normal Immunoglobulin	Date of Final Protocol: 28-Aug-2019

* Patients entering the study established on weekly SCIG infusions will have a 1-week (± 2 days) Screening Period. Patients entering the study established on every other week dosing will have a 2-week (± 2 days) Screening Period.

** Patients entering the study currently active and established on CUTAQUIG in Study SCGAM-03 will skip Stabilization Period.

Reference Therapy, Dose, Mode of Administration:

Not applicable.

Study Outcome Parameters (Primary and Secondary Endpoints):**Primary Endpoint Parameters:**

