Investigators will enroll patients into the study only after written informed consent has been obtained (and written assent where appropriate). During the Screening Period, sites must obtain written approval from Octapharma prior to patients entering the Stabilization Period (or Treatment Period, for subjects who are currently active and established on CUTAQUIG in Study SCGAM-03).

The Flow Chart of Assessments includes full details regarding all of the procedures that will be performed at each study visit. Below is a brief summary of the procedures that will be performed during the study.

Screening Period:

The Screening Visit should occur on approximately the same day the patient is scheduled to infuse with their personal SCIG product (or their final infusion of CUTAQUIG in Study SCGAM-03, if appropriate) in order to get an accurate IgG trough level. After written informed consent/assent has been obtained, patients will be evaluated for study eligibility according to the inclusion/exclusion criteria. These evaluations will include demographics, medical history, physical examinations (including body weight and vital signs), current medication use, blood and urine sample collection (for evaluation of clinical safety laboratory parameters, and IgG trough levels as specified in the Flow Chart of Assessments. Following the completion of all Screening procedures, the patient will dose with their personal SCIG

Name of Sponsor/Company: Octapharma USA, [name]	
Name of Investigational Product: CUTAQUIG	Protocol Identification Code: SCGAM-06
Name of Active Ingredient: Human Normal Immunoglobulin	Date of Final Protocol: 28-Aug-2019

product (or CUTAQUIG from Study SCGAM-03, if applicable) at their typical dose and infusion rate.

During the Screening Period (and after the infusion with their personal SCIG product or CUTAQUIG from Study SCGAM-03, if applicable), patients must not receive any other IgG product; therefore, it is anticipated that patients will receive their first dose of CUTAQUIG between 5 days and 16 days after the Screening Visit.

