Cohort 3 (every other week dosing - patients will receive CUTAQUIG every other week at the equivalent of twice their weekly body-weight dependent [mg/kg] dose): Patients will return to the clinic for the Treatment Period Baseline Visit to receive their first double mg/kg weekly dose and begin an every other week dosing schedule. Infusion volume increases when switching from weekly dosing to every other week dosing must not exceed a maximum allowed volume increase per infusion site of 25 mL/site for patients \geq 40 kg or 10 mL/site for patients $<$ 40 kg at the Treatment Period Baseline Visit. If a patient's doubling of their weekly dose requires dosing with a volume of more than the maximum allowed increase in volume per injection site (25 mL/site or 10 mL/site, dependent on patient body weight), then they will be required to increase the number of infusion sites to remain below the maximum body-weight dependent volume increase. If this occurs, after 2 infusions the patient may remove one of the newly introduced injection sites as long as the volume per injection site increase limit is not exceeded. Infusion flow rates will be determined by the patient and Investigator, but initially should not exceed the patient's prior infusion rate, nor the maximum infusion rates listed in the protocol. If a patient initially does not tolerate the dosing regimen, the Investigator should decrease the infusion rate to a tolerable rate (revising the tubing, number of injection sites, needle gauge, etc.).

Note: Patients entering must already be established on weekly dosing for a minimum of 12 weeks prior to Screening.

All Cohorts: If, during the study, a patient's body weight changes by $>5\%$ from the first infusion of IMP, the dose will be adjusted to keep a constant mg/kg body weight basis. Additional adjustments will be made if the patient's body weight changes $>5\%$ from the previous adjusted weight. In addition, individual patient doses may be titrated up or down, per Investigator discretion.

Dosing will take place on site at study visits, and otherwise at the patient's home by self-administration or with assistance (relative, caregiver, etc.). The Termination Visit must occur prior to the patient receiving any other IgG product.

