5.4 Dose and Dosing Schedule

CUTAQUIG will be administered by subcutaneous infusion either every week (± 2 days) or every other week (± 2 days) at double the weekly dose. The dosing frequency will be determined by the cohort assignment (Section 3.3.2).

A minimum interval of 4 days must be observed between 2 single subcutaneous infusions.

Patients will receive the same mg/kg body weight dose as their previous SCIG product prior to study entry that will be calculated at Screening. The dose (mg/kg) will be calculated by taking a patient's total dose in milligrams (mg) of their prior SCIG and dividing by the patient's weight (kg) at the Screening Visit. This will provide the milligrams of CUTAQUIG required. Study site personnel will use dose calculation worksheets provided by the Sponsor to determine each patient's required quantity (mg) of CUTAQUIG.

If, during the study, body weight changes by $>5\%$ from the first infusion of IMP, the dose will be adjusted to keep a constant mg/kg body weight basis. Additional adjustments will be made by the Investigator at study visits if the patient's body weight changes $>5\%$ from the previous adjusted weight. In addition, individual patient doses may be titrated up or down, per Investigator discretion.

CUTAQUIG infusions will be administered at the clinic and will be self-administered at home in between scheduled site visits.

Each study visit may deviate from the planned date; however, the deviations must not cumulate. Study visit weeks and time windows are presented in Table 7.

An individual patient's CUTAQUIG dose may be adjusted, if considered necessary by the Investigator, by titrating upward or downward; this dose adjustment should be based on the difference between the patient's measured serum total IgG trough levels while on CUTAQUIG and each patient's target serum total IgG trough level.

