6.1.1 Screening Visit

Study-related procedures will begin only after written informed consent (and assent, if appropriate) has been obtained from the patient and/or their legal guardians.

Note: Patients who participated in Study SCGAM-03 must receive their final infusion of CUTAQUIG for Study SCGAM-03 prior to being consented for Study SCGAM-06.

At the Screening Visit the following activities will be performed:

- Written (signed and dated) informed consent (and assent, if age appropriate)
- Check of inclusion and exclusion criteria
- Record demographic data
- Document medical history
- Record previous drug and non-drug therapies
- General physical examination, including body weight and vital signs
- Draw blood samples for total IgG trough level
- Draw blood samples for safety laboratory parameters
- Collect urine sample including sample for urine pregnancy test (females of childbearing potential, only)
- Infusion by the patient of their personal, commercially available SCIG product at the same body-weight dependent dose (mg/kg) and infusion flow rate (ml/hr/site) as their previous infusions; however, this flow rate should not exceed maximum infusion rates listed in protocol (Section 5.5.3). Patients who participated in Study SCGAM-03 will have already received a CUTAQUIG infusion on the same day prior to providing written informed consent (and assent, if appropriate) for Study SCGAM-06.
- Receive written approval from the Sponsor, which will include confirmation that the chosen cohort is open for enrollment, prior to entering the patient into the Stabilization Period.

It is anticipated that the patients will receive their first dose of CUTAQUIG 5 days to 16 days after the Screening Visit, depending when their last infusion occurred.

6.1.2 CUTAQUIG Stabilization Period (Stabilization Period Week 0 through Stabilization Period Week 4)

After completing the Screening Period and receiving written Sponsor Acknowledgment of the cohort assignment during the Treatment Period, patients will enter a 4-week Stabilization Period during which they will receive CUTAQUIG infusions at the same body-weight dependent (mg/kg) dose and infusion flow rate (ml/hr/site) as their previous SCIG product; however, this flow rate should not exceed maximum infusion rates listed in protocol (Section 5.5.3).

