6.1.5 Time Windows Used in this Study, including Tolerances

In this study, the following time windows and tolerances apply:

Table 7: Study Visit Times and Windows Used in this Study

Time point	Time stated	Tolerance
Stabilization Period Week 0: Cohort 1 and Cohort 2	1 week after Screening Visit	± 2 days
Stabilization Period Week 0: Cohort 3	2 weeks after Screening Visit	± 2 days
Treatment Period Baseline Visit	4 weeks after Stabilization Period Week 0	± 3 days
Treatment Period required on-site visits: Cohort 1 and Cohort 2	Weeks 4, 8, 12, and 24	± 1 week
Treatment Period required on-site visits: Cohort 3	Weeks 4, 12, and 24	± 1 week
Treatment Period optional on-site visits: all cohorts	Weeks 16, and 20	± 1 week
Interval between Last Treatment Visit and (Early) Termination Visit: Cohort 1 and Cohort 2	1 week	± 2 days (and prior to another IgG product)

Time point	Time stated	Tolerance
Interval between Last Treatment Visit and (Early) Termination Visit: Cohort 3	2 weeks	± 2 days (and prior to another IgG product)
Blood and urine sampling	Before IMP administrations conducted at the study site	none
CUTAQUIG infusions at patient's home	Every week (every 7 days), or Every other week (every 14 days) at double the weekly dose	±2 days ±2 days

Study visit days and windows/tolerances are not additive, but always refer back to the first visit time point for each study period.

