6.2 Duration of Study

6.2.1 Planned Duration for an Individual Patient

The duration for each patient in the study will be approximately 30 to 32 weeks: approximately 1 to 2 weeks in the Screening Period, 4 weeks in the Stabilization Period, 24 weeks in the Treatment Period, and 1 to 2 weeks to Termination Visit.

Patients entering the study established on weekly SCIG infusions will have a 1 week Screening Period. Patients entering the study established on every other week dosing will have a 2 week Screening Period.

Patients entering the study currently active and established on SCGAM-03 CUTIQUIG will skip the 4 week Stabilization Period.

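### Table 7 schedules Cohort 3 for a two-week gap before the first CUTAQUIG infusion, although every Cohort 3 patient is on weekly dosing; the skipped dose lowers the reference trough T_w

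*Protocol*

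**What the plan says.** Protocol Section 6.1.5, Table 7, sets the interval from Screening to Stabilization Week 0 by cohort: 1 week for Cohorts 1 and 2, and "2 weeks after Screening Visit" for Cohort 3, each ± 2 days.

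Two other places set it by the schedule the patient was on before entry. Section 6.2.1 states: "Patients entering the study established on weekly SCIG infusions will have a 1 week Screening Period", and "Patients entering the study established on every other week dosing will have a 2 week Screening Period". A footnote to Duration of Treatment in the Study Outline gives the same rule with ± 2 days, saying that patients "established on weekly SCIG infusions will have a 1-week" Screening Period.

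For Cohort 3, Section 3.3.2 states: "Patients entering must already be established on weekly dosing for a minimum of 12 weeks prior to Screening". Section 4.4 confines patients on an every-other-week schedule to Cohorts 1 and 2.

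Section 5.4 directs the reader to the table: "Study visit weeks and time windows are presented in Table 7". Section 6.1.1 expects the first CUTAQUIG dose 5 to 16 days after Screening, "depending when their last infusion occurred". After the infusion given at Screening, the Study Outline says "patients must not receive any other IgG product" for the rest of the Screening Period.

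T_w is determined after the Stabilization Period and T_eow at the final study visit (Protocol Sections 9.1 and 9.2.2; SAP Sections 5 and 9). Patients moving directly from active participation in SCGAM-03 skip Stabilization.

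**The concern.** Every Cohort 3 patient who enters Stabilization is covered by two non-overlapping windows: 12 to 16 days from Table 7, and 5 to 9 days from the Study Outline. The table seems to have been keyed to the regimen a patient is going to, not the one the patient comes from. It is also wrong for every-other-week entrants to Cohorts 1 and 2, who get 1 week instead of 2, but right for weekly entrants to those cohorts. Swapping the two rows would therefore not repair it.

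A site that follows Table 7 complies with the protocol and makes a weekly-dosed patient skip one infusion. Stabilization then repeats the usual mg/kg dose, and no make-up dose is specified. T_w is drawn after four weekly infusions, too few for IgG to recover fully. T_eow comes about six months later, when recovery is nearly complete. The error thus falls almost wholly on the reference member of the pair. It hides part of any real fall under every-other-week dosing, in the study's only confirmatory test.

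**Working it through.** **1. The plan's own sample size.** Inputs from Protocol Section 9.1: SD 3.0 g/L, within-pair correlation 0.8, margin 1 g/L, one-sided alpha 0.025, paired t-test.

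- SD of the difference = 3.0 × √(2 × (1 − 0.8)) = 1.897 g/L.
- Noncentral-t power at a true difference of 0: n = 30 gives 79.7%, n = 31 gives 81.0%.

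The stated minimum of 31 is reproduced.

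**2. Deficit left by a longer gap.** Half-life 30 to 35 days is from Protocol Section 1.1, so k = ln 2 / 30 = 0.0231 or ln 2 / 35 = 0.0198 per day. Assume weekly steady state before Screening and first-order elimination. As a share of the infused part of the trough, for a gap of g days instead of 7:

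- at Stabilization Week 0: 1 − exp(−k(g − 7));
- t days after Week 0: that value × exp(−kt).

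T_w is drawn at t = 28 and a final-visit T_eow at t = 28 + 182 = 210. For g = 14:

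| Time point | Half-life 30 d | Half-life 35 d |
|---|---|---|
| Stabilization Week 0 | 14.9% | 12.9% |
| T_w (t = 28) | 7.8% | 7.4% |
| Treatment Week 4 (t = 56) | 4.1% | 4.3% |
| Week 26 (t = 210) | 0.1% | 0.2% |

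Across Table 7's window the T_w deficit runs from 5.4% (12 days, half-life 35) to 9.8% (16 days, half-life 30). Adding first-order absorption with a peak at 2.6 to 6 days moves the upper figure to 9.9% and changes little else. At 9 days, the upper limit of the 1-week window, the deficit is 2.2 to 2.4%.

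**3. Bias in g/L.** The documents give neither a mean trough nor the share of it that comes from infusion. Assumed range: trough 5 to 12 g/L (5 is the entry floor) and 50 to 100% infused. Bias in T_w = trough × infused share × deficit, for a 14-day gap:

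- low: 5 × 0.50 × 0.0743 = 0.19 g/L;
- middle: 8 × 0.75 × 0.0782 = 0.47 g/L;
- high: 12 × 1.00 × 0.0782 = 0.94 g/L.

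**4. Effect on the test.** At a true fall of exactly 1 g/L, a bias b gives noncentrality b × √31 / 1.897. The chance of wrongly rejecting H0 is the upper tail of the noncentral t beyond 2.042 (30 df):

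| Bias per affected patient | All follow Table 7 | Half | Quarter |
|---|---|---|---|
| 0.19 g/L | 7.8% | 4.6% | 3.4% |
| 0.47 g/L | 26.6% | 9.8% | 5.2% |
| 0.94 g/L | 76.1% | – | – |

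Partial adherence is entered as a proportionally smaller mean bias. A simulation of the patient mixture at 0.46 g/L gave 25.7%, 9.6% and 5.2%, so that shortcut is adequate.

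**The case against.** The strongest objection is that harm arises only if sites followed Table 7 over two statements written specifically about the Screening Period, and the documents do not show how many did. Timing by the last infusion, as in Section 6.1.1, fits the 1-week reading. This stands as a limit on the size. It does not resolve the conflict, since 5 to 16 days allows both readings and Section 5.4 names Table 7.

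The upper type I figures are also extreme. They need all 31 patients to follow Table 7, hence no direct SCGAM-03 roll-overs, and 76% further needs a 12 g/L trough that is wholly infused. They use the gross T_w bias; subtracting the Week 26 residual turns 0.94 into about 0.92 g/L and 76% into about 74%. Where an early terminator's Treatment Week 4 trough serves as T_eow, over half of the bias cancels. These points are correct, so the figures are conditional illustrations.

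The gap would not be wholly invisible. Troughs are drawn at Screening, Week 0 and Baseline and will be listed and plotted, and a panel reviews deviations before database lock. But no planned analysis examines the interval. SAP Section 8.4 flags departures of more than 2 days from schedule; it is unclear whether it covers this gap at all, and if Table 7 is taken as the schedule, 14 days counts as on time.

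Finally, a test that excludes long intervals loses power: about 51% at n = 16, and few or no patients remain if nearly all followed Table 7. That is true, but it is a sensitivity run beside an unchanged primary test.

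**Conclusion.** The concern holds and should be fixed. The contradiction is in the current text and needs no modelling. Its direction is also firm: any Cohort 3 patient scheduled by Table 7 has a T_w that is too low, which favours concluding that troughs are maintained within 1 g/L.

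The size is conditional. The percentage deficit rests on the protocol's half-life and a simple elimination model. The range of 0.19 to 0.94 g/L per affected patient rests on the assumed trough and infused share. Type I error ranges from the nominal 2.5%, if nobody followed Table 7, through about 5 to 27% at the middle bias with quarter to full adherence, to 76% in the worst case. Trough-guided dose titration (Protocol Section 5.4) is not modelled. Direct SCGAM-03 roll-overs are unaffected, and the sample size of 31 stands.

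**What to change.** - **Protocol Table 7:** key the two Stabilization Week 0 rows to prior dosing schedule. Weekly, which includes all of Cohort 3: 1 week ± 2 days. Every other week: 2 weeks ± 2 days.
- **SAP Section 9:** for each Cohort 3 patient who entered Stabilization, derive the days from the Screening infusion to Stabilization Week 0 and report the distribution. If no interval exceeds 9 days, that closes the matter.
- **SAP Section 9:** repeat the confirmatory test without patients whose interval exceeded 9 days, keeping direct SCGAM-03 roll-overs in. State the number remaining, since power may be low.

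The cost is a wording correction to two table rows, one variable derived from visit dates already collected, and one sensitivity run. No new data are needed, and the SAP items remain possible after enrolment has closed.

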6.2 Duration of Study

6.2.1 Planned Duration for an Individual Patient

The duration for each patient in the study will be approximately 30 to 32 weeks: approximately 1 to 2 weeks in the Screening Period, 4 weeks in the Stabilization Period, 24 weeks in the Treatment Period, and 1 to 2 weeks to Termination Visit.

Patients entering the study established on weekly SCIG infusions will have a 1 week Screening Period. Patients entering the study established on every other week dosing will have a 2 week Screening Period.

Patients entering the study currently active and established on SCGAM-03 CUTIQUIG will skip the 4 week Stabilization Period.

6.2.2 Planned Duration for the Study as a Whole

The study will be considered completed when all patients have completed the Termination Visit.

The estimated study start (enrollment of first patient) is the 3rd quarter 2019. Recruitment duration is expected to be approximately 18 months; therefore, the estimated study completion (last patient last visit) is anticipated in the 1st quarter 2021.

6.2.3 Premature Termination of the Study

Both the responsible Investigators and the Sponsor reserve the right to terminate the study at any time. Should this be necessary, study close-out procedures will be arranged on an individual site basis after review and consultation by both parties. In terminating the study, the Sponsor and the Investigator will ensure that adequate consideration is given to the protection of the patients' interests.

Furthermore, the Investigator should promptly inform the IRB and provide a detailed written explanation. Pertinent regulatory authorities and IRBs will be informed in accordance with applicable regulatory requirements.

6.2.3.1 Early Termination of the Entire Clinical Study

At any time, the study as a whole will be terminated prematurely if:

- New toxicological or pharmacological findings or safety reports invalidate the earlier positive benefit-risk assessment.

- If more than 2 independent thromboembolic events (TEEs) (ie, ischemic stroke, transient ischemic attack, cerebral infarction, cerebrovascular accident, cerebral thrombosis, embolic infarctions, [acute] myocardial infarction, deep vein thrombosis, pulmonary embolism, venous thrombosis excluding thrombophlebitis) are observed fulfilling the following criteria:
 - Assessed as probably or possibly related to CUTAQUIG treatment by Investigator and/or Sponsor
 - Confirmed by the IDMC
- Any other reason rendering the continuation of the study impossible for the Sponsor

6.2.3.2 Early Termination at an Individual Study Site

At any time, the study can be terminated at an individual study site if the site:

- Cannot comply with the requirements of the protocol
- Cannot comply with applicable standards
- Does not meet the required recruitment rate

Should the study be prematurely terminated, all study materials, including IMP, must be returned to the Sponsor.

